### **16.1.3. Action Taken with Investigational Products**

Should the Investigator need to alter the administration of the study drug from the procedure described in the protocol due to the well-being and safety of the patient then the action taken will be recorded on the AE eCRF page, as one of the following options:

- Dose Reduced
- Drug Interrupted
- Drug Withdrawn
- Not Applicable
- Other

### **16.1.4. Outcome**

Outcome of an AE will be recorded on the AE eCRF as follows:

- Recovered/Resolved or attributable to other (defined) cause
- Recovering/Resolving
- Recovered/Resolved with Sequelae
- Not Recovered/Not Resolving, up to a 30-day follow-up period for treatment-related AEs
- Fatal
- Unknown (or patient lost to follow-up after 4 attempts at contact over a period of 30 days)

## **16.2. Definition of Serious Adverse Event**

An SAE is an AE occurring during any study phase (i.e., baseline, treatment, washout, or follow-up), and at any dose of the study drug (active or placebo), that fulfills one or more of the following:

- Results in death.
- It is immediately life-threatening.
- It requires in-patient hospitalization or prolongation of existing hospitalization.
- It results in persistent or significant disability or incapacity.
- Results in a congenital abnormality or birth defect.
- It is an important medical event that may jeopardize the patient or may require medical intervention to prevent one of the outcomes listed above.

Important medical events that may not be one of the above may be considered an SAE by the Investigator when, based upon appropriate medical judgment, they are considered clinically significant and may jeopardize the patient, or may require medical or surgical intervention to prevent one of the outcomes listed above.

An AE is considered “life-threatening” if, in the opinion of either the Investigator or the Sponsor, its occurrence places the patient at immediate risk of death. It does not include an AE that, had it occurred in a more severe form, might have caused death.

### **16.2.1. Notification of a Serious Adverse Event**

All SAEs regardless of relationship to the IP during the period starting from the time of informed consent through the follow-up visit, will be recorded in the eCRF. Once the Investigator becomes aware of an SAE, they must report the SAE to the Clinical Research Organization (CRO) Safety Department within 24 hours of knowledge of the event.

A written SAE report must include a full description of the event including the below parameters (include any protocol specific requirements):

- Diagnosis or description of event
- Onset date
- Severity assessment
- Causal relationship to the IP
- Assessment of seriousness of the event
- Corrective treatment administered for the SAE
- Action taken related to IP including the following: dose interruption, dose delay, dose reduction, or IP discontinuation
- Outcome of event and end date

Follow-up information for SAEs and information on non-serious AEs that become serious should also be reported to the CRO Safety Department as soon as information is available.

As further information regarding the SAE becomes available, such follow-up information should be documented on a new SAE report form, marked as a follow-up report, scanned, and emailed to the address at the bottom of the report form.

Withdrawal from the study in the event of an SAE and therapeutic measures taken shall be at the discretion of the Investigator. A full explanation for the discontinuation from the study should be made in the patient’s medical records and in the eCRF.

### **16.3. Clinical Laboratory Abnormalities and other Abnormal Assessments as Adverse Events and Serious Adverse Events**

Abnormal laboratory findings (e.g., hematology, serum chemistry, coagulation, and urinalysis) or other abnormal assessments (e.g., ECG and vital signs) per se are not reported as AEs. However, those abnormal findings that are deemed **clinically significant** or are associated with signs and/or symptoms must be recorded as AEs if they meet the definition of an AE (and recorded as

an SAE if they meet the criteria of being serious) as previously described. Clinically significant abnormal laboratory or other abnormal findings that are detected after consent or that are present at baseline and worsen after consent are included as AEs (and SAEs if serious).

The Investigator should exercise their medical and scientific judgment in deciding whether an abnormal laboratory finding or other abnormal assessment is clinically significant. Usually, the abnormality should be associated with a clinically evident sign or symptom or be likely to result in an evident sign or symptom in the near term, to be considered clinically significant. A clinically significant laboratory abnormality in the absence of clinical symptoms may jeopardize the patient and may require intervention to prevent immediate consequences. For example, a markedly low serum glucose concentration may not be accompanied by coma or convulsions yet be of a magnitude to require glucose administration to prevent such sequelae.

#### **16.4. Recording Adverse Events**

AEs spontaneously reported by the patient and/or in response to an open question from the study personnel or revealed by observation will be recorded in accordance with the Investigator's normal clinical practice and on the AE page of the eCRF during the study at the investigational site.

However, abnormal values that constitute an SAE or lead to discontinuation of administration of study drug must be reported and recorded as an AE. Information about AEs and SAEs will be collected from the time of consent until the end of the study. The AE term should be reported in standard medical terminology when possible. For each AE, the Investigator will evaluate and report the onset (date and time), resolution (date and time), intensity, causality, action taken, serious outcome (if applicable), and whether or not it caused the patient to discontinue the study. AEs that occur during the study must be documented in the patient's medical record, on the AE eCRF, and on the SAE report form. If an SAE report is completed, pertinent laboratory data should be recorded on the SAE form, preferably with baseline values and copies of laboratory reports.

In addition, if the abnormal assessment meets the criteria for being serious, the SAE form must also be completed. A diagnosis, if known, or clinical signs or symptoms if the diagnosis is unknown, rather than the clinically significant laboratory finding or abnormal assessment, should be used to complete the AE/SAE page. If no diagnosis is known and clinical signs or symptoms are not present, then the abnormal finding should be recorded.

It is important to distinguish between serious and severe AEs. Severity is a measure of intensity whereas seriousness is defined by the criteria under Section 16.2. An AE of severe intensity may not be considered serious.

Pregnancy itself is not regarded as an AE unless there is a suspicion that a study drug may have interfered with the effectiveness of a contraceptive medication.

The outcome of all pregnancies (spontaneous miscarriage, elective termination, normal birth, or congenital abnormality) must be followed up and documented even if the patient was discontinued from the study.

All reports of congenital abnormalities/birth defects are SAEs. Spontaneous miscarriages should also be reported and handled as SAEs. Elective abortions without complications should not be handled as AEs.

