**Table 10. Hematological Adverse Events Dose Adjustment Guidance**

	Dose modification
ANC <math>\geq</math> 1.0 mm^3	No dose modification
0.5 < ANC < 1.0 mm^3	Stop LYT-100, repeat blood test in 48-72 hrs, or at a clinically indicated time interval, and when resolved to ANC>1.0 then resume at 500mg BID for 3 days followed by 750mg BID  If the same AE repeats, stop LYT-100, repeat blood test in 48-72 hrs, or at a clinically indicated time interval, and when resolved to ANC>1.0 then resume at 500mg BID  If the same AE repeats, discontinue LYT-100 permanently
ANC < 0.5 mm^3	Discontinue LYT-100 permanently
Hgb <math>\leq</math> 8.5 g/dL	Stop LYT-100, clinically manage as appropriate and when Hgb > 10.0 resume LYT-100 at 500mg BID for 3 days followed by 750MG BID  If the same AE repeats, permanently discontinue LYT-100
Platelets > 100,000 mcL	No dose modification

Platelets 50,000-100,000 mcL	
Stop LYT-100 until resolved to >100,000 then resume at 500mg BID for 3 days followed by 750mg BID
 
If the same AE repeats, stop LYT-100, repeat blood at a clinically indicated time interval, and when resolved to >100,000 then resume at 500mg BID
 
If the same AE repeats, discontinue LYT-100 permanently

Platelets < 50,000 mcL	
Stop LYT-100 until resolved to >100,000 then resume at 500mg BID for 3 days followed by 750mg BID
 
If the same AE repeats, permanently discontinue LYT-100

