### Hepatic Impairment

No dose modifications are needed for AST and/or ALT elevation  $\leq 3$  x the upper limit of normal (ULN) without symptoms or hyperbilirubinemia.

If a patient exhibits  $>3$  but  $\leq 5$  x the upper limit of normal (ULN) ALT and/or AST without symptoms or hyperbilirubinemia after starting LYT-100 therapy:

- Discontinue any potential confounding co-medications, exclude other causes, and monitor the patient closely.
- Repeat liver chemistry tests as clinically indicated.
- Dose reduce to 500 mg BD until resolved to  $\leq 3$  x upper limit of normal (ULN) ALT and/or AST with subsequent re-titration to the full dosage as tolerated.

If a patient exhibits  $>3$  but  $\leq 5$  x ULN ALT and/or AST accompanied by symptoms or hyperbilirubinemia:

- Permanently discontinue LYT-100. Do not rechallenge patient with LYT-100.

If a patient exhibits  $>5$  x ULN ALT and/or AST:

- Permanently discontinue LYT-100. Do not rechallenge patient with LYT-100.

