### **21.4.3. Laboratory Evaluations**

Laboratory evaluations (including hematology, serum chemistry, coagulation, and urinalysis) will be listed and summarized by treatment and by protocol specified collection time point. This will be done both for actual observed laboratory values and for changes from baseline.

The abnormal urinalysis results (dipstick and microscopy), if applicable, will be listed only.

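### A laboratory value that triggers a Section 9.5 dose reduction or interruption is not automatically an AE, so the AE record and its link to the dose change depend on each investigator's judgment

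*Combined protocol and SAP*

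**What the plan says.** **When dosing changes on a laboratory value.** Under Hepatic Impairment, Section 9.5 orders a dose reduction for ALT and/or AST above 3 and up to 5 times ULN "without symptoms or hyperbilirubinemia after starting LYT-100 therapy". Under Renal Impairment it orders a reduction at a creatinine clearance of 30 to 50 mL/min. Table 10 orders a stop and later restart at set ANC, hemoglobin and platelet thresholds. For the intermediate ANC band, for example, it says "Stop LYT-100, repeat blood test in 48-72 hrs, or at a clinically indicated time interval".

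**When a value becomes an AE.** Section 16.3 sets the default: abnormal laboratory findings "or other abnormal assessments (e.g., ECG and vital signs) per se are not reported as AEs". Findings that are clinically significant or come with symptoms "must be recorded as AEs if they meet the definition of an AE". Clinical significance is the investigator's call: "Usually, the abnormality should be associated with a clinically evident sign or symptom", or be likely to produce one soon. Section 16.4 removes that discretion in two cases: "abnormal values that constitute an SAE or lead to discontinuation of administration of study drug must be reported and recorded as an AE".

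**Where a dose change is written down.** Section 16.1.3 says that if the investigator has to alter administration for the patient's safety, "then the action taken will be recorded on the AE eCRF page, as one of the following options". The options include dose reduced, drug interrupted and drug withdrawn.

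**What is tabulated.** Laboratory results "will be listed and summarized by treatment and by protocol specified collection time point" (Section 21.4.3), and Section 21.2 adds shift tables.

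**The concern.** The rule that compels an AE record and the rules that change the dose have different thresholds. Section 9.5 acts on values that may cause no symptoms, and for transaminases it makes their absence a condition. Section 16.4 compels an AE only for an SAE or a discontinuation. Between the two lies a group of patients whose dosing was changed by protocol because of a laboratory value, and whose value becomes an AE only if the investigator judges it clinically significant.

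Safety and tolerability is the primary endpoint, and a dose change forced by a laboratory finding is a direct measure of tolerability. Two sites following the text correctly could record the same event differently. Section 9.4 makes elevated liver enzymes an AE of special interest that may prompt an ad hoc committee meeting, but gives no recording rule to support this. Section 7.2.2 reports more raised gamma-glutamyl-transpeptidase (high dose) and more decreases in white cells (low dose) on pirfenidone than on placebo in the Japanese study, and Section 7.3 expects pirfenidone's AEs with LYT-100. Any under-recording could therefore fall more on the active arm and make the arms look more alike.

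**Working it through.** The plan gives no figure on this point and made no formal sample size calculation (Section 21.1), so there is nothing to reproduce. The check is a comparison of texts, with one calculation for scale.

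**Step 1. Triggers against the recording rules.**

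| Trigger in Section 9.5 | Action ordered | AE compelled by 16.4 (if not an SAE)? | Called an AE elsewhere? |
|---|---|---|---|
| ALT/AST >3 to ≤5 × ULN, symptom-free | Reduce, then re-titrate | No | Liver enzymes named as an AE of special interest (9.4), with no recording rule |
| CLcr 30–50 mL/min | Reduce, then re-titrate | No | No |
| ANC between 0.5 and 1.0 | Stop, then resume | Only if a temporary stop counts as discontinuation | Yes: Table 10's title and its recurrence wording |
| Hgb ≤ 8.5 g/dL | Stop, then resume | Same | Yes |
| Platelets 50,000–100,000 and below 50,000 | Stop, then resume | Same | Yes |

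**Step 2. Does discontinuation cover the other actions?** Section 16.1.3 offers reduction, interruption and withdrawal as separate options. Section 16.2.1 lists interruption, delay, reduction and discontinuation separately. The better reading is that Section 16.4 does not reach temporary stops. Since it does not define discontinuation as permanent, a wider reading is possible, but even that leaves dose reductions uncovered.

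**Step 3. Does Section 16.3 fill the gap?** It can, because it accepts that a value may be significant without symptoms. It does not make a dose change a criterion. For the hepatic rule, the patient by definition has no symptoms, and this is where the usual test points away from significance.

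**Step 4. Other records of the dose change.** Capsule counts (Section 11.3) and the diary (Section 9.1.1) can show that doses were missed. Neither is said to capture the laboratory reason.

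**Step 5. Outputs.** The AE listing and summaries in Section 21.4.2 do not include action taken. Section 21.2 plans summaries of days and concentration of exposure, but names no table of dose reductions or interruptions. Unscheduled tests go to the local laboratory (Section 15.1.6), whereas Section 21.4.3 summarizes by scheduled time point. In Table 5, chemistry is drawn at every on-treatment clinic visit, so an ALT/AST trigger would ordinarily be a scheduled value. Hematology on treatment is drawn only at Weeks 1, 4, 12 and 26. A cytopenia found in the 26 − 12 = 14 weeks between the last two draws would be an unscheduled value.

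**Step 6. Scale.** With 25 patients per arm (Table 7), one unrecorded patient is 1/25 = 4.0 percentage points. The chance of at least one laboratory-driven dose change in an arm is 1 − (1 − p)^25, where p is an assumed per-patient rate:

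| Assumed p | Expected patients, 25p | Chance of at least one |
|---|---|---|
| 2% | 0.5 | 1 − 0.98^25 = 39.7% |
| 5% | 1.25 | 1 − 0.95^25 = 72.3% |
| 10% | 2.5 | 1 − 0.90^25 = 92.8% |

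These figures say how often the situation might arise. They do not say how often it would go unrecorded.

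**The case against.** The strongest reply is that the protocol already provides for these events.

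- **Significant findings must be AEs.** Section 16.1 puts clinically significant laboratory findings inside the AE definition, Section 16.3 makes recording them mandatory, and Section 16.4 tells sites to enter the abnormal finding itself when there is neither a diagnosis nor a symptom. This stands. A reader might infer from Section 16.4 alone that only SAEs and discontinuations need an AE record, and that inference is wrong. What remains is that significance is left to judgment and a dose change does not settle it.
- **Table 10 already calls its triggers AEs.** This also stands, so the rules are not all affected alike. For hematology the defect is a contradiction with Section 16.3 rather than silence. It has a consequence: Table 10's recurrence steps refer back to an earlier AE that may not have been recorded.
- **Section 16.1.3 may itself require an AE-page entry for any safety-driven change.** This is arguable. However, the sentence concerns departures from the procedure in the protocol, and a Section 9.5 change is part of that procedure.
- **The abnormality is not lost.** Laboratory parameters are part of the primary endpoint and are listed, summarized and shown in shift tables. Section 9.4 also has the Safety Review Committee consider laboratory abnormalities separately from AEs. This stands and limits the concern to the AE and its link to the dose change.
- **The eCRF and the SAP announced in Section 21 may capture dose changes elsewhere.** They were not among the documents supplied, so this cannot be ruled out.

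**Conclusion.** The mismatch is real but narrower than it may first appear. No text makes a value that triggers a Section 9.5 reduction or interruption an AE automatically. For symptom-free hepatic and renal reductions, recording rests on the investigator's judgment. For the hematology thresholds, Table 10 and Section 16.3 use the word AE inconsistently and must be reconciled.

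A reader might go further and infer that such events vanish from the safety results. The documents do not support that: scheduled values still reach the laboratory outputs. What can be missing is the AE, the reason for the dose change, and the tie between them. Unscheduled local results can also fall outside the summaries by time point.

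The size cannot be derived from the documents, which give neither a rate of laboratory-driven dose changes nor a rate of non-recording. Each unrecorded patient moves an arm's percentage by 4 points. The conclusion assumes that discontinuation in Section 16.4 excludes dose reduction, and that the eCRF has no separate dose-change form. The point should be fixed because the remedy is cheap and the primary endpoint would depend less on site practice.

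**What to change.** 1. **Sections 16.4 and 16.3.** Require that any abnormal value leading to reduction, interruption or discontinuation of study drug be recorded as an AE with the Section 16.1.3 action taken. Put the matching exception in Section 16.3 and align both with the AE wording of Table 10.
2. **Section 21.4.3.** Tabulate each patient's worst on-treatment value by arm, including unscheduled and local-laboratory results.
3. **Section 21.4.2.** Add a by-arm summary and a listing of dose reductions, interruptions and discontinuations with the reason for each. Without this, even a fully recorded AE would not show the dose change in the outputs now named.

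The cost is a few sentences in the protocol, a line in the eCRF Completion Guidelines, and a few additional tables and listings. The downside is that a few more laboratory AEs will be listed, some of them unrelated to drug. None of this alters a dosing rule, and no view is taken on the thresholds or actions in Section 9.5.

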## **16.5. Reporting Adverse Events**

Any SAEs considered possibly or probably related to the study drug and discovered by the Investigator at any time after the study should be reported. All SAEs must be reported to the Sponsor and/or the CRO Safety Department within 1 business day of the first awareness of the event. The Investigator must complete, sign and date the SAE pages, verify the accuracy of the information recorded on the SAE pages with the corresponding source documents, and send a copy to the Sponsor and/or CRO Safety Department.

Additional follow-up information, if required or available, should all be emailed to the Sponsor and/or CRO Safety Department within 1 business day of receipt and this should be completed on a follow-up SAE form, placed with the original SAE information, and kept with the appropriate section of the eCRF and/or study file.

The Sponsor is responsible for notifying the relevant regulatory authorities of certain events. It is the Investigator's responsibility to notify the IRB/IEC of all SAEs that occur at their site in accordance with the IRB/IEC SAE reporting policy. The Investigator will also be notified of all unexpected, serious, drug-related events that occur during the clinical trial. The investigational site is responsible for notifying its IRB/IEC of these additional SAEs.

## **16.6. Follow-up of Adverse Events and Serious Adverse Events**

All AEs and SAEs that are deemed related, possibly related, or probably related to the study drug must be followed until resolution, until the condition stabilizes, until the event is otherwise explained, or until the patient dies or is lost to follow-up. The Investigator is responsible to ensure that follow-up includes any supplemental investigations as may be indicated to elucidate as completely as practical the nature and/or causality of the AE/SAE. This may include additional laboratory tests or investigations or consultation with other health care professionals.

The Sponsor may request that the Investigator perform or arrange for the conduct of supplemental measurements and/or evaluations. If a patient dies during participation in the study or during a recognized follow-up period, the Sponsor should be provided with a copy of any post-mortem findings, including histopathology.

## **16.7. Randomization Code Break**

An electronic Interactive Web Response System (IWRS) will be utilized to perform patient randomization (and stratification) using a master randomization list. Therefore, in the event of an emergency and the identification of an individual patient's treatment must be unblinded, the treatment blind for that specific patient can be broken within the IWRS system and made available to appropriate site personnel immediately. A complete audit trail of unblinding will be available within the IWRS.

## 17. ASSESSMENT OF EFFICACY

Efficacy will be assessed in an exploratory fashion. In general, efficacy will be based on changes from baseline to each post-baseline visit (through the end of treatment at Week 26). The following parameters will be measured at all study visits (except the Screening visit):

- Limb water content, by Bioelectrical impedance spectroscopy (BIS): Multiple frequency BIS (L-dex) provides accurate relative measures of protein-rich fluid in the upper limb of patients. BIS is a non-invasive technique that involves passing an extremely small electrical current through the body and measuring the impedance (or resistance) to the flow of this current. The electrical current is primarily conducted by the water containing fluids in the body. BIS quantifies the amount of protein-rich fluid in lymphedema by comparison of the affected to the non-affected limb.
- Limb volume (perometry): Relative limb volume is measured by perometry. Perometry is a non-invasive technique involving a Perometer (Pero-System), which uses infrared light to scan a limb and obtain measurements of the limb's circumference. The truncated cone tape measure method can be used as a backup if the Perometer is unavailable, or not working at time of the patient visit.
- Tissue dielectric constant (MoistureMeterD): The TDC measures the local tissue water content under the skin at various depths ranging from skin to subcutis. The results are converted into a 0% to 100% scale to reflect subcutaneous fluid deposition that can occur in early stage lymphedema.
- Tissue firmness (tonometry/SkinFibroMeter): A tonometer device is pressed into the skin to measure the amount of force required to make an indent in the tissue. The resulting measurement gauges the degree of firmness or fibrosis (tissue scarring) under the skin to assess the severity of lymphedema. (*r*) at dorsal surface of arm 10 cm below the elbow.
- Visual analog scales for pain, swelling, discomfort, and function: This graphic scale has a straight line with endpoints of 0 and 10 that is marked by the patient to calibrate to their extreme limits of pain, swelling, discomfort and function, ranging from “not at all” to “as bad as it could be”. The higher marks on the line indicates the worse condition.

Additionally, health-related QoL assessments will be collected to assess the following:

- LYMPH-Q ([Appendix 2](#)): This is a patient completed questionnaire that measures the degree of symptoms, function, and psychological impact with patients who have upper extremity lymphedema. Symptoms are rated on a 15-item scale (severe, moderate, mild to none) to measure how the arm feels, the function portion is measured on a 12-item scale (extremely difficult, moderately difficult, a little difficult and not at all difficult) to determine arm function capability, and the psychological portion is measured on a 12-item scale (always, often, sometimes, never) to evaluate how a patient feels having lymphedema.
- LYMQOL ([Appendix 3](#)): This is a patient completed questionnaire that assesses upper limb lymphedema and symptoms, and ability to perform common functional

activities in patients with BCRL. It addresses the following four domains – Symptoms, Body Image/Appearance, Function, and Mood. Each item is scored as 1 = Not at all; 2 = A little; 3 = Quite a bit; and 4 = A lot. Total scores for each domain are summed and divided by the total number of completed question responses. The overall QoL item ranges from 1 to 10. Lower scores indicate a higher QoL.

- Patient Interviews: Patients will be asked to participate in the qualitative interviews. The interviews will occur during screening and/or after completion of blinded treatment. The sample size was elected to be in line with best practice recommendations for cognitive debriefing of existing measures to provide evidence of content validity. Participants recruited for qualitative interviews will match the main inclusion and exclusion criteria found in the trial protocol (BCRL patients that have at least 6 months and no more than 15 years since the most recent type of breast cancer related surgery, have unilateral upper arm lymphedema no greater than 4 years).

The interviews will begin with concept elicitation using a set of open-ended questions that ask the patients to spontaneously identify the BCRL symptoms and daily activity impacts they experience. These data will be compared with the content of the existing instruments to determine whether they are complete and relevant in this target population.

After the open-ended portion of each interview is completed, interviewers will cognitively debrief the BCRL-specific questionnaires included in the current trial protocol. These questionnaires are LYMPH-Q and LYMPHQOL. Participants will be asked to comment on the content of each questionnaire including the clarity of the instructions and the understandability and relevance of each item and its response options.

- 

Infection due to cellulitis and lymphangitis will be reported as an AE.

- When noted, the Australian Lymphology Association’s Infection/ Cellulitis Form will also be completed (see [Appendix 4](#)).

